4.3 General Guidelines for Other Participating Institutions

Eligible participants will be entered on study centrally at Dana-Farber Cancer Institute by the Study Coordinator and research Nurse. All sites should call the Study Coordinator and research Nurse to verify treatment availability.

Following registration, participants should begin protocol treatment within 72 hours or as soon as possible. Issues that would cause treatment delays should be discussed with the Principal Investigator. If a participant does not receive protocol therapy following registration, the participant's protocol status must be changed. The Study Coordinator should be notified of participant status changes as soon as possible.

Except in very unusual circumstances, each participating institution will order the study agent(s) directly from the supplier. A participating site may order the agent(s) only after the initial IRB approval for the site has been forwarded by the Coordinating Center to the supplier.

5. TREATMENT PLAN

Treatment will be administered on an outpatient basis. Expected toxicities and potential risks as well as dose modifications for pazopanib and everolimus are described in Section 6 (Expected Toxicities and Dosing Delays/Dose Modifications). No investigational or commercial agents or therapies other than those described below may be administered with the intent to treat the participant's malignancy other than described in the inclusion/exclusion criteria.

Phase I dose escalation schema

	Dose Level	Pazopanib	Everolimus
	-1	400 mg PO QD	5 mg PO QD
Starting dose→	0	600 mg PO QD	5 mg PO QD
	+1	600 mg PO QD	10 mg PO QD
	+2	800 mg PO QD	10 mg PO QD
	+2A	800 mg PO QD	5 mg PO QD

* Dose level +2A is only to be used if the MTD is exceeded on dose level +2.

5.1 Expansion Cohort

The dose for the expansion cohort is listed below:

Agent	Dose	Route	Schedule	Cycle Length
Pazopanib	400 mg	Oral	Daily	28 days
Everolimus	5 mg	Oral	Daily	(4 weeks)

5.2 Pre-treatment Criteria

5.2.1 Screening evaluation

Within 28 days prior to start of treatment

- Complete physical examination
- Complete medical history and demographics
- Karnofsky or ECOG performance status
- Record concomitant medications
- Disease assessments: Baseline CT or MRI of the abdomen and pelvis and CT or X-ray of the chest. In patients with osseous lesions, bone X-rays and/or bone scans should be obtained.

Within 14 days prior to start of treatment

- Evaluation of vital signs including pulse, respiratory rate, body weight, and height
- Two blood pressure measurements should be taken at least 5 minutes apart
- Urine beta-HCG pregnancy test for women of childbearing potential
- Electrocardiogram

- Urinalysis, urine protein, and urine creatinine
- Laboratory assessments. Screening laboratory testing performed within 7 days of initiation of study therapy may be used for cycle 1 day 1.
 - Complete blood count with differential and platelets
 - Comprehensive Metabolic Panel including: sodium, potassium, chloride, bicarbonate, BUN, creatinine, calcium, alanine aminotransferase, aspartate aminotransferase, alkaline phosphatase, total bilirubin, albumin
 - Magnesium, phosphorus, LDH, amylase, lipase, thyroid stimulating hormone
 - Total cholesterol ≤ 300 mg/dL AND fasting triglycerides $\leq 2.5 \times$ institutional ULN.
 - Fasting lipid panel
 - Screening for hepatitis C (using quantitative RNA-PCR) and hepatitis B using serological markers (HBsAg, HBsAb, and HBCAb) for all patients.
 - Prothrombin time (PT) or international normalized ratio (INR) $\leq 2 \times$ institutional upper limit of normal (ULN) unless patients are on therapeutic anticoagulation with warfarin
 - Partial thromboplastin time (PTT) $\leq 1.5 \times$ institutional ULN unless patients are on therapeutic anticoagulation with warfarin

5.2.1 Day 1 every cycle

The following will be undertaken prior to initiating study therapy and on day 1 of every subsequent cycle:

- Vital signs including blood pressure, pulse, respiratory rate and body weight. Height will be recorded on cycle 1, day 1 only.
- Karnofsky or ECOG performance status
- Complete physical examination and toxicity evaluation (CTCAE v 4.0)
- Update concomitant medications
- Complete blood count with differential and platelets
- Comprehensive Metabolic Panel: sodium, potassium, chloride, bicarbonate, BUN, creatinine, calcium, alanine aminotransferase, aspartate aminotransferase, alkaline phosphatase, total bilirubin, albumin
- Magnesium, phosphorous, LDH, amylase, lipase, thyroid stimulating hormone
- Fasting lipid panel
- Urine pregnancy test in women of childbearing potential (at screening and cycle 1 day 1 only)
- Urinalysis
- Urine protein & creatinine
- EKG (for cycles 1-2 only)

5.2.2 Cycles 1-2 day 15

The following will be undertaken day 15 of cycles 1 and 2:

- Vital signs including blood pressure, pulse, respiratory rate, body weight, and height
- Karnofsky or ECOG performance status
- Complete physical examination and toxicity evaluation (CTCAE v 4.0)
- Update concomitant medications
- Compete blood count with differential and platelets
- Comprehensive Metabolic Panel: sodium, potassium, chloride, bicarbonate, BUN, creatinine, calcium, alanine aminotransferase, aspartate aminotransferase, alkaline phosphatase, total bilirubin, albumin
- Magnesium, phosphorous, LDH

5.2.4 Every 8 weeks

Radiologic disease evaluation: Radiological assessments include a CT or X-ray of the chest and abdominal and pelvic CT or MRI scan. In patients with osseous lesions, bone X-rays and/or bone scans should be obtained. Tumor measurements should occur every 8 weeks (within 7 days prior to day 1 of the subsequent cycle).

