1. OBJECTIVES

1.1 Study Design

This is a Phase I study with an expansion cohort in advanced urothelial cancer patients. The Phase I portion of the study will be an open-label standard 3+3 dose escalation study to determine the maximum tolerated dose (MTD) of the combination of pazopanib (GW786034) and everolimus in patients with solid tumors who have no standard treatment options available. Starting doses will be set at everolimus 5 mg PO QD and pazopanib 400 mg PO QD. Cycle length will be 4 weeks. One dose de-escalation will be allowed if the MTD is exceeded in dose level 0 (indicated as dose level -1). Initial phase I testing identified pazopanib 400 mg PO daily and everolimus 5 mg PO daily as the MTD. Based on the phase I response data, an expansion cohort of 25 patients with metastatic urothelial cancer who have received prior chemotherapy, but no prior mTOR or VEGF inhibitors, will be enrolled.

The protocol is being amended to accrue urothelial carcinoma patients rather than kidney cancer patients in the expansion cohort given the significant unmet need in urothelial carcinoma and findings of significant activity of the regimen in at least a subset of urothelial carcinoma patients,

The primary endpoint of the expansion cohort will be objective response proportion with secondary endpoints including safety, progression-free survival, and duration of response.

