6.3 Dose Modifications/Delays

6.3.1 General dose modification/Delays

Dose modifications for toxicities not otherwise covered in section 6.2 are listed in the table below. Patients who do not recover to grade 2 or less toxicity within 28 days will be removed from protocol therapy except where noted (ie. pneumonitis). In addition, patients may hold study intervention (pazopanib and everolimus) for greater than 28 days if the patient's physician and the overall principal investigator, [name], agree that the patient is deriving clinical benefit from the study drugs. Dose modifications for specific toxicities are covered in sections 6.2 and 6.3.

All toxicities, both during the DLT period and after it has been completed, will follow the guidelines laid out here in sections 6.2 and 6.3.

For definition of a Dose Limiting Toxicity, refer back to section 5.4.

Non-hematological toxicity

Toxicity	Actions
Non-Infectious Pneumonitis	Please refer to section 6.2.3
Reactivation of HBV or HCV flare	Please refer to section 6.2.4
Non-hematological toxicity Grade 2 (except pneumonitis – refer to section 6.2.3) (except hypertension, proteinuria, venous or arterial thrombosis, QTc prolongation- refer to section 6.3.2) (except hepatotoxicity – refer to section 6.3.3) (except elevated amylase and lipase- refer to section 6.3.5)	If the toxicity is tolerable to the patient, maintain the same dose. If the toxicity is “intolerable” to patient, interrupt pazopanib and everolimus until recovery to grade ≤ 1 . Then reintroduce pazopanib and everolimus at same dose. If event returns to “intolerable” grade 2, then interrupt pazopanib and everolimus until recovery to grade ≤ 1 . Then reintroduce pazopanib and everolimus at one dose level lower. If event is recurrent “intolerable” grade 2 despite two dose reductions, discontinue pazopanib and everolimus.
Grade 3 or 4 (except hyperlipidemia ¹) (except pneumonitis – refer to section 6.2.3) (except hypertension, proteinuria, venous or arterial thrombosis, QTc prolongation- refer to section 6.3.2) (except hepatotoxicity – refer to section 6.3.3)	Interrupt pazopanib and everolimus until recovery to grade ≤ 1 . Then reintroduce pazopanib and everolimus at one dose level lower. No more than 2 dose reductions allowed.
Stomatitis / oral mucositis / mouth ulcers	See section 6.2.3 Management of stomatitis / oral mucositis / mouth ulcers

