9. STUDY CALENDAR

Scans must be done ≤ 4 weeks prior to the start of therapy. In the event that the participant's condition is deteriorating, laboratory evaluations should be repeated within 48 hours prior to initiation of the next cycle of therapy.

All assessments must be performed prior to administration of any study medication. All study assessments and medications should be administered within ± 3 days of the protocol-specified date, unless otherwise noted.

9.1 Phase I:

		Treatment cycles			
	Screening ¹	Cycles 1, 2		Subsequent cycles	Off Study
		Day 1	Day 15	Day 1	
Informed Consent	X				
History	X	X	X	X	
Concurrent meds	X	X	X	X	
Physical exam (Ht, Wt, BSA)	X	X	X	X	X
Vital Signs	X	X	X	X	
Performance Status	X	X	X	X	X
CBC with differential/platelets	X	X	X	X	X
EKG	X	X	B		
Urinalysis, urine protein & creatinine ²	X	X		X	
Serum chemistry ³	X	X	X	X	X
Fasting Lipid Panel	X	X		X	X
Qualitative β-HCG ⁴	X	X		X	
Hepatitis B and C screen ⁵	X				
Pazopanib		X-----X			
Everolimus		X-----X			
Adverse event evaluation		X-----X		X	
Tumor measurements	X		A	A	X
Radiologic evaluation	X		A		X

1. Screening labs may be used as cycle 1 day 1 labs if performed within 7 days of initiation of study therapy.
 2. If UPC ≥ 1 then a 24 hour urine protein must be assessed.
 3: Albumin, alkaline phosphatase, total bilirubin, calcium, fasting glucose, LDH, phosphorus, total protein, SGOT [AST], SGPT [ALT], serum sodium, potassium, chloride, bicarbonate, BUN, magnesium, uric acid, amylase, lipase, thyroid stimulating hormone (day 1 of each cycle only).
 Monitor serum liver tests before initiation of treatment with pazopanib and at weeks 3, 5, 7 and 9. Thereafter, monitor at Month 3 and Month 4, and as clinically indicated. Periodic monitoring should continue after Month 4. Urine or serum pregnancy test (women of childbearing potential) at screening and day 1 of each cycle (+/- 3 days).
 5. Screening for hepatitis B : Prior to registrations, patients will be tested for hepatitis B viral load and serologic markers, HBV-DNA, HBsAg, HBs Ab, and HBc Ab. Patients with risk factors for hepatitis C should be tested using quantitative RNA-PCR

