9.2 Expansion cohort

Test/Procedure	Screening		Treatment Cycles 1, 2 (28 day cycles)		Subsequent cycles (28 day cycles)	Off Study 28 days after last dose (+/- 7 days) ⁹	Survival
	-28 days	-14 days	Day 1 ¹ (±3 days)	Day 15 (±3 days)	Day 1 (±3 days)		
Informed Consent	X						
History	X		X	X	X	X	
Concurrent Medications	X		X	X	X	X	
Physical Exam	X		X	X	X	X	
Vital Signs		X	X	X	X	X	
Performance Status	X		X	X	X	X	
CBC with Differential/ Platelets		X	X	X	X	X	
Amylase and lipase		X	X		X		
EKG		X	X				
Urinalysis, Urine Protein & Creatinine ²		X	X		X	X	
Serum Chemistry ³		X	X	X	X	X	
TSH		X	X		X		
PT/INR, PTT		X					
HbA1c ⁷		X					
Fasting Lipid Panel		X	X		X	X	
Qualitative β-HCG ⁴		X	X				
Hepatitis B and C Screen ⁸		X					
Pazopanib			X-----X				
Everolimus			X-----X				
Adverse Event Evaluation			X-----X		X	X	
Radiologic Evaluation ^{5,6}	X				X	X	
Survival Follow-Up							X

1. Cycle 1 Day 1 evaluations are to be conducted within 1-week prior to start of protocol therapy. Screening labs may be used as Cycle 1 Day 1 labs if drawn within 7 days of initiating study therapy.
 2. If UPC ≥ 1, then a 24 hour urine protein must be assessed.
 3. Albumin, alkaline phosphatase, total bilirubin, calcium, fasting glucose, total protein, SGOT [AST], SGPT [ALT], serum sodium, potassium, chloride, bicarbonate, BUN, uric acid, magnesium, LDH, phosphorus
 4. Urine pregnancy test (women of childbearing potential) at screening and cycle 1 day 1 only.
 5. Radiological imaging should occur every 8 weeks, following cycle 1 day 1.
 6. If scans have been performed within 30 days before coming off treatment, they do not need to be repeated as an off-study assessment. If scans cannot be obtained (e.g. patients coming off treatment to go to hospice or patients have died), please document in study file.
 7. Applies to patients with uncontrolled diabetes mellitus
 8. Screening for hepatitis: Prior to registrations, all patients will be tested for hepatitis B serologic markers (HBsAg, HBs Ab, and HBc Ab, HBV-DNA) and for hepatitis C (using quantitative RNA-PCR)
 9. This visit can be foregone for patients who are too unwell to attend or for other reasons at the investigator's discretion. Patients may be contacted by phone to assess resolution of toxicities and may be contacted for survival follow up.

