10. MEASUREMENT OF EFFECT

Objective response rate is the primary endpoint of the expansion cohort of this trial and participants will be assessed by RECIST v1.1 criteria. For the purposes of this study, participants should be reevaluated every 8 weeks. In addition to a baseline scan, confirmatory scans should also be obtained at least 4 weeks following initial documentation of an objective response.

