14.4 Analysis of Secondary Endpoints

Phase I:

Pharmacokinetic parameters will be analyzed to determine whether pharmacologically significant drug interactions are present between everolimus and pazopanib. The concentration of everolimus in whole blood and plasma will be determined using a validated assay involving high performance liquid chromatography with electrospray ionization mass spectrometric detection. Time points will be determined as the difference between the midpoint of the blood collection interval and starting time of dose administration. Concentration-time profiles will be analyzed by noncompartmental methods and/or nonlinear least squares regression using Professional version 4.0.1 software package (Pharsight Corp., Cary, NC). Pharmacokinetic parameters and

variables will be calculated according to standard equations. Descriptive summaries of PK parameters (C_{trough}, T_{1/2} and C_{max}) will be provided by dose cohort.

Secondary

Secondary endpoints will evaluate safety, progression-free survival (PFS), overall survival (OS) and duration of response. Duration of response is calculated for objective responders and defined as the time in months from the first observation of a response (e.g., the first time that the appropriate RECIST 1.1 criteria was observed for confirmed responders) to the first documented progression or death due to any cause, whichever occurs first. Duration of response is censored at the date of last disease evaluation for patients who are known to be alive and who have not relapsed after a CR or PR.

Progression-free survival is calculated as the months between registration and documented PD as determined by RECIST 1.1, or death due to any cause, whichever occurs first. Overall survival is defined as the time in months from registration to death due to any cause or, censored at the date last known alive. Patients alive without disease progression will be censored at the date of last disease evaluation. Time to event data will be estimated with the Kaplan-Meier method. Efficacy will further be described by 4- and 12-month PFS and OS rates along with 90% CIs. Descriptive statistics will be used to characterize the disease and previous treatment features as well as the details of protocol therapy.

Toxicity

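### Scan timing has two anchors and two windows, and the plan does not say which governs after a dose hold; the 4-month PFS rate has only 9.75 days of slack

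*Combined protocol and SAP*

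**What the plan says.** **Scan timing.** Section 5.2.4: "Tumor measurements should occur every 8 weeks (within 7 days prior to day 1 of the subsequent cycle". Section 9.2, footnote 5: "Radiological imaging should occur every 8 weeks, following cycle 1 day 1". The on-treatment imaging mark in the 9.2 table stands under subsequent cycles, Day 1 (±3 days). Section 10 gives the interval with no cycle anchor: "For the purposes of this study, participants should be reevaluated every 8 weeks". Section 9 sets a general window: "All study assessments and medications should be administered within ± 3 days of the protocol-specified date, unless otherwise noted". Section 1.1: "Cycle length will be 4 weeks".

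**Holds.** Section 6.3.1: "Patients who do not recover to grade 2 or less toxicity within 28 days will be removed from protocol therapy except where noted". It also states that "patients may hold study intervention (pazopanib and everolimus) for greater than 28 days" if the treating physician and the overall principal investigator agree that there is benefit.

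**Use of the scan dates.** Section 14.4: "Efficacy will further be described by 4- and 12-month PFS and OS rates along with 90% CIs". Progression and the end of response are dated by RECIST 1.1 assessment. Section 14.4 counts PFS from registration; section 10.1.6 counts it from start of treatment. Section 4.1 lets DF/HCC institutions start treatment up to 14 days after registration.

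**The concern.** One passage ties the scan to the start of the next cycle and the other to a fixed date. Sites can therefore follow different rules in good faith. Even with no delay, a scan can satisfy one window and miss the other.

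The larger issue is a dose hold. If a site treats day 1 of the next cycle as a restart visit after recovery and times imaging by section 5.2.4, the scan moves with the hold. Progression is then found later in patients who had toxicity, and PFS and duration of response depend partly on toxicity and on which passage the site follows. The 4-month PFS rate is the most exposed figure because the week-16 scan falls shortly before it. The cohort has a single arm, so no comparator is scanned under the same rule. Scan dates cannot be corrected afterwards.

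**Working it through.** The documents give no figure for 4-month PFS, so there is none to reproduce. The design figures in section 14.1 (early stopping 0.734 and type I error 0.099 at a 10% response rate, power 0.904 at 30%) do reproduce by exact binomial calculation: 0.7338, 0.0995 and 0.9037. They do not use PFS.

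**1. Windows with no delay** (days elapsed since cycle 1 day 1)

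| Scan | Section 5.2.4 (-7 to 0) | Section 9.2 (±3) |
|---|---|---|
| Week 8 | 49-56 | 53-59 |
| Week 16 | 105-112 | 109-115 |

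Counting cycle 1 day 1 as day 1, the week-8 windows are study days 50-57 and 54-60.

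**2. Slack before the landmark.** 4 months = 4 × 365.25/12 = 121.75 days.
- Late edge of 5.2.4: 121.75 - 112 = 9.75 days, so a shift of 10 days crosses.
- Early edge: 121.75 - 105 = 16.75 days, so a shift of 17 days crosses.
- A 28-day shift puts the scan at days 133-140.

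**3. Size, if a hold moves cycle day 1.** These inputs are assumptions, not document figures: exponential progression with median 3 months (91.3125 days), every event dated at the detecting scan, a share q = 0.20 to 0.40 of patients held for d days between the first and second scans.

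S(t) = 0.5^(t/91.3125), so S(49) = 0.6894, S(56) = 0.6537, S(105) = 0.4507, S(112) = 0.4273, S(119) = 0.4052 and S(121) = 0.3991.

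The reported 4-month rate is S at the last scan before day 121.75. The change is q × [S(last scan before 121.75 with the hold) - S(week-16 scan without it)].

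| Hold and position in the 5.2.4 window | Difference in S | Change, q = 0.20 to 0.40 |
|---|---|---|
| 7 days, late edge | 0.4052 - 0.4273 = -0.022 | -0.4 to -0.9 points |
| 14 days, early edge (scan at day 119) | 0.4052 - 0.4507 = -0.046 | -0.9 to -1.8 |
| 16 days, early edge (scan at day 121) | 0.3991 - 0.4507 = -0.052 | -1.0 to -2.1 |
| 14 days, late edge (scan at day 126) | 0.6537 - 0.4273 = 0.226 | +4.5 to +9.1 |
| 14 days, scans spread evenly over the window | average of the above cases | +2.4 to +4.9 |
| 17 days or more, late edge | 0.6537 - 0.4273 = 0.226 | +4.5 to +9.1 |
| 17 days or more, early edge | 0.6894 - 0.4507 = 0.239 | +4.8 to +9.5 |

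A delayed scan that still falls before the landmark finds more progressions and lowers the rate. One that passes the landmark raises it.

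**4. Time origin.** If PFS runs from registration and treatment starts 14 days later, the nominal week-16 scan is at 112 + 14 = day 126, and at day 129 with a +3-day window. Both are past 121.75 with no hold at all.

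**5. Scale.** An exact 90% confidence interval for 13 of 26 patients is 0.33 to 0.67.

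**The case against.** The strongest reply is that this is an ambiguity, not two rival schedules. Section 5.2.4 itself says every 8 weeks, cycles are 28 days, and every rule gives the same nominal day when nothing is delayed. The 9.2 calendar is partly cycle-based too, and the 7-day window can be read as one of the exceptions that section 9 allows. All of this stands. A reader might infer that the two sections contradict each other outright; they do not.

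Second, no passage says that a hold postpones day 1 of the next cycle. Pazopanib is dosed continuously (section 5.3.1), section 6.3 speaks of interrupting and reintroducing drug rather than restarting cycles, and the Phase I rule in section 5.4.1 counts missed days inside cycle 1. That leans towards a running clock, in which case only the window mismatch remains. It does not settle the expansion cohort: section 5.4.1 concerns dose-limiting toxicity in dose escalation, section 5.6 refers to treatment delays for adverse events, and section 9 refers to initiating the next cycle.

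Third, a reader might infer that holds always inflate PFS. The table above shows that they do not: short holds, and 14-day holds at the early edge, lower it slightly. Deaths also count as PFS events and are not dated by scans, so the model overstates the scan-dated share.

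Fourth, the endpoint is descriptive, and the shift is small beside its confidence interval. That limits the priority of the point, but the interval does not account for a systematic shift in scan dates.

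**Conclusion.** The point holds as a gap in the scan rule. The anchors and windows differ, and the plan does not say which governs after a hold. A delay is possible, not prescribed: it requires a site to let the hold move cycle day 1. In that case the week-16 scan passes the 4-month landmark after a shift of 10 to 17 days or more, measured from treatment start, and holds of that length are allowed.

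Under the assumed inputs the 4-month PFS rate changes by about -2 to +9.5 points. The sign and size depend on hold length and position in the window. Duration of response is exposed to the same mechanism but was not quantified. The primary response rule and its error rates are unaffected.

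The documents do not support a claim that PFS will be inflated, or that fixing the scan anchor alone protects the landmark. With registration as origin, the permitted start gap can carry the week-16 scan past 4 months without any hold.

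**What to change.** - **Scan rule (5.2.4 and 9.2 footnote 5).** State one rule in both: imaging at weeks 8, 16, 24 and so on, counted from cycle 1 day 1, with one window, not shifted for dose holds or cycle delays. Remove the tie to day 1 of the subsequent cycle.
- **PFS origin (10.1.6 and 14.4).** Use one origin in both.
- **Early PFS rate (14.4).** Beside the 4-month rate, report a rate at a time after the latest allowed week-16 scan, measured from the chosen origin. With a +3-day window, that means after day 115 from treatment start, or after day 129 from registration with a 14-day start gap. Once scans are fixed, 4 months from treatment start already meets this by 121.75 - 115 = 6.75 days; 4 months from registration does not. From registration, 20 weeks (day 140) would: it is later than day 129 and earlier than the first possible week-24 scan (168 - 7 = day 161, if the window opens 7 days early).

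The cost is wording in the two scan passages, the PFS definitions and one line of 14.4, with no extra scheduled scans. The downside is that some scans will fall during a hold rather than at a restart visit.
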